### **3.2.6 36-Week Per Protocol Population**

The 36-Week Per Protocol Population will include all MRI-PDFF Evaluable patients who have a Week 36 MRI-PDFF measurement, and a baseline and Week 36 liver biopsy.

The 36-Week Per Protocol Population will be used to assess robustness of the analysis of hepatic fat fraction results of MRI-PDFF during the 36-Week period.

Additional potential patients may be excluded from Week 36 Per Protocol Population if the patients:

- Take any prohibited concomitant medication during 12-36 week Treatment Period; or
- Patients who are <=75% compliant over the course of the 12-36 week Treatment Period and/or the period between Week 30 – 36.

Please note that non-compliance from Week 30-36 is not per protocol for Week 36 laboratory tests and Week 36 MRI-PDFF; non-compliance between Week 30-36 with drug compliance for Weeks 12-36 >75% are per protocol for liver biopsy.

For patients who are in the Week 36 Per Protocol Population with Week 36 liver biopsy measured more than two weeks of last dose date, these liver biopsy values will not be used in the Week 36 Per Protocol analysis for liver biopsy responders.

### **3.2.7 Safety Population**

The Safety Population will include all patients who are randomized in the study and receive at least 1 dose of study drug and will be used for all safety analyses. The Safety Population is identical to the ITT Population.

### **3.3 Patient Disposition**

The reason given for each screen failure will be summarized and listed. Patient disposition will be provided for all randomized patients. The number and percentage of patients in each of the following disposition categories will be presented:

- Patients who are randomized,
- Patients who start study drug,
- Patients who have PK assessment at Week 2,
- Patients who complete the 12-week Treatment Period,
- Patients who complete the 36-week study,
- Patients who withdraw from the study during the 12-week Treatment Period, and
- Patients who withdraw from the study.

For randomized patients who withdraw from the study, the primary reason for the withdrawal will be listed and summarized.

The number of patients included in each analysis population will be summarized.

### **3.4 Demographics and Baseline Characteristics**

Demographics (age, sex, race, and ethnicity), body weight, height, and BMI will be summarized by randomized treatment using descriptive statistics for the randomized patients based on the Safety Population. Age group (<65 years versus  $\geq$ 65 years), age group by median ( $\geq$ median versus <median), and BMI category ( $\geq$ 30 kg/m^2 versus <30 kg/m^2) will also be summarized. Other disease characteristics include diabetes and hypertension status.

Baseline levels of FT4, FT3 and TSH will be summarized to evaluate hypothyroidism. Baseline liver enzymes (ALT, AST), and NAS from liver biopsy will also be summarized for disease characteristics, as well as PNPLA3 and baseline fibrosis score category (0/1 and 2/3).

Medical history will be coded using the Medication Dictionary for Regulatory Activities (MedDRA). The number and percentage of patients with medical history will be summarized by their MedDRA preferred term within system organ class and by treatment.

### **3.5 Prior/Concomitant Medications**

The use of any prior medication and concomitant medication will be listed for the Safety Population with an indication of whether the medication was prior or concomitant during the study.

Medications will be coded using the most recent version of World Health Organization (WHO) Drug Dictionary. The number and percentage of patients taking each concomitant medication will be summarized by preferred term within Anatomical Therapeutic Chemical (ATC) classification and by treatment group for the Safety Population. Concomitant medication is defined as any medication taken on or after the first dose day of study medication.

### **3.6 Study Medication Exposure and Compliance**

Days of exposure to study medication will be summarized by treatment group for the Safety Population using descriptive statistics. Exposure in days is defined as the date of last dose of study drug minus the date of first dose of study drug plus 1. In addition, a contingency table will be provided to display the number and percentage of patients with exposure in the following categories:

- 1 to  $\leq$ 2 weeks (1-14 days),
- $>2$  to  $\leq$ 4 weeks (15-28 days),
- $>4$  to  $\leq$ 8 weeks (29-56 days);
- $>8$  to  $\leq$ 12 weeks (57-84 days),
- $>12$  to  $\leq$ 36 weeks (84-252 days), and
- $>36$  weeks (253 days or more).

Compliance will be calculated based on the total actual number of capsules taken as compared to the total expected number of capsules taken (2 per day). Percent compliance with the study medication during the 12-week Treatment Period (from Week 4 through Week 12) and the whole 36-week Treatment Period (from Week 4 through Week 36) will be summarized by treatment group for the Safety Population using descriptive statistics. Additionally, the number and percentage of patients within each treatment group with overall compliance in the following categories: <80%, 80% to 120%, and >120%, will be provided.

All the patients randomized to the active study drug group will take MGL-3196 80 mg. Based on the PK assessment and SHBG at Week 2, the dose at Week 4 may stay at 80 mg, it may be increased to 100 mg, or it may even be reduced to 60 mg. At Week 8 visit, the dose may be reduced to 40 mg. Duration of each dose level will be summarized, and number/percentage of patients taking each dose at each visit will be tabulated.

### **3.7 Analysis of Efficacy**

#### **3.7.1 Descriptive Statistics**

All available raw and derived data will be listed for the randomized patients. Descriptive statistics of the baseline, change from baseline and/or percent change from baseline to each post-baseline visit will be presented by treatment group for each efficacy measurement for the ITT population.

#### **3.7.2 Analyses of Hepatic Fat Fraction by MRI-PDFF**

Summary statistics (number of patients, mean, standard deviation, median, minimum, and maximum) for hepatic fat fraction by MRI-PDFF at all visits and percent change from baseline will be provided for the MRI-PDFF Evaluable Population.

Analyses of hepatic fat fraction will be performed based on the MRI-PDFF Evaluable population and repeated based on the 12-Week Per Protocol population.

The primary efficacy endpoints are summarized and analysed by treatment group (MGL-3196 vs. placebo) by overall population and subgroups. For overall analysis and certain subgroups, the primary efficacy endpoints will also be analysed by MGL-3196 exposure level. The

MGL-3196 exposure levels are determined by the plasma MGL-3196 concentration at Week 2 and later visits to represent the overall MGL-3196 exposure level for patients.

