2 STUDY OBJECTIVES

2.1 Primary Objective

The primary objective of this study is to determine the effect of once-daily oral MGL-3196 80 mg versus placebo (randomized 2:1) for 12 weeks on the percent change in hepatic fat fraction by proton density fat fraction magnetic resonance imaging (MRI-PDFF) from baseline in patients with biopsy-proven NASH.

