10 STATISTICS

10.1 Analysis Populations

The Intent-to-Treat (ITT) Population will include all patients who are randomized in the study and receive at least 1 dose of study drug. The ITT Population will be used for all efficacy analyses.

The Per Protocol Population will include all ITT patients who finish the Week 12 visit with valid MRI-PDFF measurements and do not have any major protocol deviations. Patients who are <80% compliant over the course of the initial 12-week Treatment Period will not be included in the Per Protocol Population.

The Safety Population will include all patients who are randomized in the study and receive at least 1 dose of study drug and will be used for all safety analyses.

Demographics, disposition, and study populations will be summarized descriptively.

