10.2 Statistical Methods

10.2.1 Analysis of Efficacy

10.2.1.1 Primary efficacy analysis

The primary efficacy variable will be the percent change in MRI-PDFF from baseline to Week 12. Summary statistics (number of patients, mean, standard deviation, median, minimum, and maximum) at all visits and change from baseline will be provided. The primary efficacy analysis will be analyzed with an analysis of covariance (ANCOVA) model with treatment as a factor. For any patients in the ITT Population with a missing primary efficacy parameter, the control (placebo)-based pattern mixture model will be used. Based on PK obtained in healthy volunteers dosed for up to two weeks on doses of MGL-3196 from 20-200 mg per day, a significant fraction of patients randomized to an 80 mg dose may have their dose reduced to 60 mg after PK assessment at Week 2. The multiplicity (MGL-3196 60 mg versus placebo and MGL-3196 80 mg versus placebo) will be controlled by Dunnett's Test. The primary efficacy analysis will be performed based on the ITT Population and repeated based on the Per Protocol Population.

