### **3.2.3 MRI-PDFF Evaluable Population**

The MRI-PDFF Evaluable population includes all patients who were randomized in the study, received study drug, finished Week 12 Visit, with valid MRI-PDFF measurements at both baseline and Week 12 Visit.

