### **3.2.5 12-Week Per Protocol Population**

The 12-Week Per Protocol Population will include all MRI-PDFF Evaluable patients who do not have any major protocol deviations during the first 12 weeks. The following criteria will be evaluated for major deviations prior to unblinding of the treatment allocation:

- No eligibility criterion violations;
- Did not discontinue study drug prior to Week 12;
- Patients who are <=75% compliant over the course of the initial 12-week Treatment Period and/or the period between Week 8 and Week 12;
- Not taken any prohibited concomitant medication during 12-week Treatment Period;
- Not unblinded during the 12-week double-blind treatment period; and
- No other substantial protocol violations during 12-week Treatment Period.

The 12-Week Per Protocol Population will be used to assess robustness of the analysis of hepatic fat fraction results of MRI-PDFF during the 12-week Treatment Period.

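### The SAP replaces the protocol's ITT, placebo-imputed Week 12 primary analysis with one on patients who have both scans, gives no reason, and keeps no inferential ITT analysis of that endpoint

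*SAP*

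**What the plan says.** **Protocol.** Section 10.1 states: "The ITT Population will be used for all efficacy analyses". Section 10.2.1.1 applies this to the Week 12 percent change in MRI-PDFF and sets the missing-data rule: "For any patients in the ITT Population with a missing primary efficacy parameter, the control (placebo)-based pattern mixture model will be used". It repeats the analysis in the Per Protocol Population, and the synopsis agrees. It also handles dose: "The multiplicity (MGL-3196 60 mg versus placebo and MGL-3196 80 mg versus placebo) will be controlled by Dunnett's Test".

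**SAP.** Section 3.7.2 reads: "Analyses of hepatic fat fraction will be performed based on the MRI-PDFF Evaluable population and repeated based on the 12-Week Per Protocol population". Membership of the Evaluable population (3.2.3) requires patients to have finished the Week 12 visit "with valid MRI-PDFF measurements at both baseline and Week 12 Visit". The second population is nested in the first (3.2.5): "The 12-Week Per Protocol Population will include all MRI-PDFF Evaluable patients who do not have any major protocol deviations". The model in 3.7.2.1 has treatment as its only term, compares all active patients with placebo, reports a 95% confidence interval, and imputes nothing.

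**What remains of ITT.** SAP 3.7.1 gives descriptive statistics "for each efficacy measurement for the ITT population". SAP 3.7.4.4 uses ITT for the fibrosis markers. The mITT, LOCF and optional MMRM analyses of MRI-PDFF in 3.7.2.5 concern Week 36.

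**The concern.** The two documents specify different primary analyses, and the SAP does not say so. Its version history does not mention the change of population. Its introduction promises to report departures from the SAP, which does not cover the SAP's own departures from the protocol.

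The protocol analysis keeps every dosed patient and treats a missing active patient as a placebo patient. The SAP analysis in effect takes missing active patients to respond like observed ones. The only repeat is on a subset of the same patients, so it cannot test that assumption. At stake is whether the declared primary result, which Amendment 6 reports as achieved, can be shown to hold under the missing-data rule that the protocol chose.

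**Working it through.** **Plan's own figure.** With 36 per group, difference 30, SD 35 and two-sided alpha 0.025, SE = 35 × sqrt(2/36) = 8.25. The noncentral t power is 90.8%, against the stated 90%. The sample size is sound and the point does not depend on it.

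**Who is left out.** Inputs: the Safety Population counts in the Amendment 6 adverse event table (41 placebo, 84 active), which SAP 3.2.7 says is identical to ITT, and the Evaluable counts in Amendment 6 Table 3.2 (38 and 78).

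| | ITT | Evaluable | Left out |
|---|---|---|---|
| Placebo | 41 | 38 | 3 (7.3%) |
| Active | 84 | 78 | 6 (7.1%) |
| Total | 125 | 116 | 9 (7.2%) |

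**Shift in the estimate.** Let A and P be the observed active and placebo means. With a treatment-only model, placebo-based imputation and many imputations, the ITT active mean tends to (78A + 6P)/84 and the placebo mean stays at P. The difference is therefore (78/84)(A − P) = 0.929(A − P).

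- Missing active patients respond like placebo: -30 becomes -27.9, and -20 becomes -18.6.
- They keep half the effect: factor (78 + 3)/84 = 0.964, so -30 becomes -28.9.
- They keep all of it: no change.

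**Power and significance.** Evaluable SE = 35 × sqrt(1/38 + 1/78) = 6.92. Because the ITT estimate is a fixed multiple of the Evaluable one, its true sampling SE scales as well: 0.929 × 6.92 = 6.43. The ratio of estimate to SE is then essentially unchanged.

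Rubin's rules do not follow that scaling. In simulation (SD 35, placebo mean 0, 30 imputations, 4,000 trials per effect) the sampling SE of the ITT estimate was about 6.4 to 6.5 and the mean Rubin SE about 6.9 to 7.0. Under no effect, the Rubin test rejected in about 3.5% of trials and the Evaluable test in 5.2%. Power at two-sided 0.05 (the last two columns come from separate runs):

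| True difference | Evaluable | ITT, Rubin SE | ITT, sampling SE |
|---|---|---|---|
| -30 | 99.2% | 98.9% | not run |
| -20 | 80.8% | 76.5% | 79.7% |
| -15 | 57.0% to 57.8% | 49.9% | 57.5% |

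With Rubin's SE, only an Evaluable estimate between about -13.7 (1.98 × 6.92) and -14.8 (1.98 × 6.96/0.929) would change sides at 0.05. With the sampling SE that band all but disappears.

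**The case against.** The best case against is that this is mainly a documentation gap. Missingness is low, balanced, and below the 10% dropout that the sample size allowed for. The sample size was itself set on patients reaching Week 12. Placebo-based imputation is an assumption too, and section 10.2.1.1 of the protocol names the model without a variance method. All of this stands and limits the weight of the point. It does not supply the missing reason or the missing analysis.

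A reader might infer more, in four ways that the documents do not support:

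- **That the population was chosen after seeing results.** SAP 1.0 is listed as approved on 15 May 2018, after the November 2017 tables. But those tables already use the Evaluable population, and the SAP says it is written for Amendment 4 of 2 August 2017. When the choice was made cannot be seen. Nor can it be seen whether an ITT run existed, because Amendment 6 shows only redacted excerpts.
- **That this is an analysis of patients who completed treatment.** SAP 3.1 accepts scans up to three weeks after the last dose, and staying on drug to Week 12 is a separate Per Protocol criterion in 3.2.5. Evaluable means having both scans.
- **That dropping Dunnett's test is an error.** The pooled contrast compares the arms as randomised and fits the primary objective, which is "once-daily oral MGL-3196 80 mg versus placebo (randomized 2:1) for 12 weeks". It needs recording, not reversing.
- **That the 0.025 in SAP section 4 contradicts the 95% interval.** It is a sizing input carried over from the protocol. The alpha for the single contrast should simply be stated.

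**Conclusion.** The discrepancy is clear from the text: the protocol's population and missing-data method for the primary endpoint are gone from the SAP, without explanation, and nothing inferential on ITT replaces them. It should be fixed.

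The size is modest. Nine of 125 patients are affected, and the estimate would move at most about 7% toward zero if missing active patients did no better than placebo. That rests on the Amendment 6 counts and an imputation model without covariates; the power figures also assume SD 35 in both arms and two-sided tests. It would be tempting to read the power table as a real loss of several points at smaller effects. Almost all of that comes from Rubin's variance being conservative here, not from the change of population. The results are redacted, so bias in the reported result is not shown.

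**What to change.** In SAP 3.7.2 and 3.7.2.1, specify as primary the Week 12 percent change on the ITT Population, pooled active versus placebo, with missing values imputed under the protocol's placebo-based pattern mixture model. State the variance method, the number of imputations and the seed. Label the MRI-PDFF Evaluable and 12-Week Per Protocol analyses supportive. This applies the protocol's population and imputation to the SAP's contrast; it does not restore the protocol's analysis in full.

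If the sponsor keeps the Evaluable analysis as primary, give the reason and add the ITT placebo-based analysis as a specified sensitivity analysis.

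In either case, add a paragraph to the SAP and study report recording the change of population, of imputation, and of dose comparison (Dunnett to pooled), with the reason and the date relative to the November 2017 readout. State the alpha that applies to the single pooled contrast.

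Cost: SAP wording, a short imputation program, one report paragraph, and probably a slightly less favourable estimate. No new data are needed.

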Rationale: Results of the 12 week MRI-PDFF primary endpoint readout of MGL-3196-05 have now been obtained in 116 patients treated with MGL-3196 or placebo who had both a baseline and Week 12 MRI-PDFF. The study remains blinded to individual patient treatment code. The primary endpoint was achieved. MGL-3196 treated patients versus placebo treated patients demonstrated [REDACTED] relative fat fraction reduction compared to [REDACTED] reduction in placebo [REDACTED] (see Table 1, supporting statistical data beginning on Page 8). A prespecified group of MGL-3196 treated patients [REDACTED] with higher MGL-3196 drug levels [REDACTED] demonstrated [REDACTED] fat reduction relative to placebo [REDACTED] of all MGL-3196 treated and [REDACTED] of the higher drug level group as compared with [REDACTED] of placebo patients attained $\geq 30\%$ liver fat reduction. Patients with lower drug exposure (MGL-3196, < 2700 ng*hr/ml) had less response [REDACTED] [REDACTED], significant relative to placebo [REDACTED]. The exposure groups were based on projected AUCs after dose adjustment, and an exposure of ≥ 2700 ng*hr/ml was chosen based on Phase 1 data that showed that there was a pharmacodynamic effect to lower lipids at this exposure.

There were statistically significant reductions in liver enzymes (ALT, AST) within the drug-treatment group that were also statistically significant relative to placebo in the group [REDACTED] of MGL-3196-treated patients with higher drug levels. Lipids, including LDL-cholesterol, triglycerides, apolipoprotein B and lipoprotein(a) were also significantly reduced in MGL-3196 treated compared to placebo patients. Triglyceride lowering appeared to be significantly attenuated at 12 weeks following the dose reduction at 4 weeks [REDACTED]

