Prespecified high ($\geq 75\%$ increase from baseline) SHBG group (biomarker for MGL-3196 hepatic levels) showed similarly enhanced improvement in MRI-PDFF and liver enzymes relative to placebo. Overall safety has been good with mostly mild AEs and some moderate AEs which are generally balanced between placebo and treatment group. There have been 3 SAEs, blinded to treatment code, none of which are considered related to study drug by independent Medical Monitor ([REDACTED]) or Sponsor. More than 30 patients have now had a follow up 36 week liver biopsy; although the NASH scoring is blinded, study pathologist, [REDACTED], who reads the 36 week biopsies on an ongoing basis, has not reported any findings of non-NASH or biliary lesions (Page 2 of scoring sheet “Any non-NASH findings” is not blinded).

Table 1. Results of Week 12 Primary Endpoint Analysis

	ALL MGL-3196	High MGL-3196 ¹	Low MGL-3196	Placebo
Number of patients	[REDACTED]	[REDACTED]	[REDACTED]	[REDACTED]
Primary Endpoint:				
Relative change in MRI-PDFF (% change from baseline, median)				
Significance relative to placebo	[REDACTED]	[REDACTED]	[REDACTED]	[REDACTED]
Percentage of patients attaining $\geq 30\%$ liver fat reduction	[REDACTED]	[REDACTED]	[REDACTED]	[REDACTED]
Significance relative to placebo	[REDACTED]	[REDACTED]	[REDACTED]	[REDACTED]

¹ Prespecified MGL-3196 exposure groups ≥ 2700 ng*hr/ml and < 2700 ng*hr/ml

MGL-3196-05 Amendment 6 adds a minor dose adjustment (increase in dose of 20-25%) in a small percentage (~10) of patients still completing the 36 week Main study, who have low exposure on doses of 60-80 mg (low predose exposure, low SHBG response).

[REDACTED]
Several parameters and visits were assessed to assure that the data were not impacted by compliance issues (e.g. not taking drug the day before visit, taking drug prior to visit).

[REDACTED] SHBG levels (blinded to patient ID) were reviewed because SHBG has a long half-life, and may be a marker for average drug exposure. Any dose adjustments will be made by unblinded personnel.

In patients remaining in the Main study or randomized to MGL-3196 who meet criteria and consent to Extension study:

Table 2. Doses in Main and Extension Study in Patients Assigned to MGL-3196 in the Main Study

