** PCPDFF = Percent change in MRI-PDFF from Baseline to Week 12  **
** Trt = Treatment group                                         **
*****
PROC GLM data=EFF;
  CLASS Trt;
  MODEL PCPDFF = Trt;
  LSMEANS Trt / e diff cl;
RUN;
```

In this analysis, the treatment group will be either MGL-3196 active or placebo. A pairwise comparison will be performed between MGL-3196 active and placebo. LS means for the treatment difference, 95% confidence interval and p-value will be provided.

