#### 3.7.2.4 Subgroup Analyses for Week 12 Primary Efficacy Endpoints

The analyses of percent change and absolute change in hepatic fat fraction will be performed for the MRI-PDFF Evaluable population for the following subgroups:

- Gender (male, female);
- Weight loss from Screening ( $< 5\%$  weight loss at Week 12,  $\geq 5\%$  weight loss at Week 12);
- Ethnicity (Hispanic or Latino, Not Hispanic or Latino);
- Type 2 diabetes (yes or no);
- PNPLA3 SNP phenotype (homozygous, heterozygous, negative);
- Fibrosis Stage [0-1 (Total), 2-3];
- NAS Score ( $\leq 4$ ,  $> 4$ );
- Week 12 SHBG group ( $\geq 75\%$ ,  $< 75\%$  change from baseline to Week 12);
- Baseline liver fat percentage ( $< 20\%$ ,  $\geq 20\%$ ); and
- Exposure group (AUC  $< 2700$  ng\*hr/mL, AUC  $\geq 2700$  ng\*hr/mL).

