## **4. SAMPLE SIZE DETERMINATION**

Approximately 117 patients in total will be randomized to 80 mg (2/3) or placebo (1/3) treatments. After PK assessment, a significant fraction of patients' combined AUC (MGL-3196 plus MGL-3196-M1) may exceed 5500 ng\*hr/ml resulting in a dose reduction to 60 mg. In order to power the study appropriately for an efficacious dose (which may be  $\geq 80$ mg), randomization may continue until approximately 36 patients have continued at Week 4 on the 80 mg dose. It is estimated that the treatment difference of percent change in hepatic fat fraction from baseline to Week 12 between any dose of MGL-3196 and the placebo group is about -30%. With a common standard deviation for the percent change in hepatic fat fraction at 35%, 36 patients per group completing the Week 12 visit will provide 90% power with a 2-sample t-test. The significance level is set as 0.025 for the consideration of multiplicity in comparisons of 2 daily dosing regimens of MGL-3196 versus the placebo group. The enrollment size is designed to allow for 10% drop out before the Week 12 visit, and as such, patients who drop out of the study will not be replaced.

With the sample size of 39 patients per treatment, the power for selected secondary efficacy endpoints was calculated. The baseline hepatic fat fraction is expected to be approximately 15% to 17%, thus the change from baseline to Week 12 in hepatic fat fraction is approximately -5.5% when comparing to placebo. With common standard deviation of change in hepatic fat fraction as 6%, 36 completed patients will provide 94% power for the study when evaluating the treatment effect in change of hepatic fat fraction.

In addition, the sample size is expected to provide meaningful liver biopsy-related data.

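### Drug-exposure groups, formed after randomisation and only in treated patients, are tested against the whole placebo arm on MRI-PDFF change; randomisation does not protect that contrast

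*SAP*

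**What the plan says.** SAP 3.7.2 sets up the exposure analysis of the primary endpoint: "For overall analysis and certain subgroups, the primary efficacy endpoints will also be analysed by MGL-3196 exposure level". It also says that "MGL-3196 exposure levels are determined by the plasma MGL-3196 concentration at Week 2 and later visits". The Amendment 6 rationale in the protocol describes the grouping a little differently: "The exposure groups were based on projected AUCs after dose adjustment". It calls the groups prespecified and takes the 2700 ng*hr/ml cut from Phase 1 lipid data.

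SAP 3.7.2.4 then says: "The analyses of percent change and absolute change in hepatic fat fraction will be performed for the MRI-PDFF Evaluable population for the following subgroups". The list that follows mixes baseline factors (gender, ethnicity, diabetes, baseline fibrosis, baseline liver fat) with factors that arise after randomisation. The latter include the AUC group and the "Week 12 SHBG group" (at least 75% versus less than 75% change from baseline). SAP 3.7.2.6 repeats the exposure split at Week 36, with an SHBG split at 88% based on mean SHBG after Week 12.

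SAP 3.7.2.4 and 3.7.2.6 do not name the placebo comparator. For exposure, the tables under the Amendment 6 rationale do. Table 3.2.1 sets N=44 (AUC 2700 or above) and then N=34 (below 2700) against placebo N=38, each with an LS mean difference, 95% CI and p-value. Table 3.3.1 does the same with odds ratios for a fat reduction of 30% or more. For SHBG, the rationale says only that the high group "showed similarly enhanced improvement in MRI-PDFF and liver enzymes relative to placebo".

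A related design is explicit elsewhere. SAP 3.7.3 (biopsy) and SAP 3.7.4.4 (fibrosis markers) compare treated patients who reached an MRI-PDFF response with all placebo patients.

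The main comparison is different. In SAP 3.7.2.1, "the treatment group will be either MGL-3196 active or placebo".

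**The concern.** Randomisation makes all active patients comparable with all placebo patients. It does not make a subset of active patients, picked by drug levels after treatment began, comparable with an unselected placebo arm. Placebo patients have no AUC, so no matching placebo stratum can be formed. After dose adjustment, a patient's AUC also partly reflects the titration rule, which itself uses Week 2 AUC and SHBG. Prespecifying the cut fixes the threshold but does not remove the selection.

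If characteristics that influence drug handling also influence liver fat, the high and low groups will differ from placebo in opposite directions even with an inert drug. That is the pattern a reader would take as evidence of exposure-response. The Amendment 6 rationale cites the exposure-group results, and it says dosing data from this study will support dose selection for later studies. SAP 3.7.2 does not describe these contrasts as exploratory or non-randomised; the exploratory wording is in SAP 3.7.3 and 3.7.4.

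**Working it through.** **Inputs from the documents**

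- Planning difference 30 points ("between any dose of MGL-3196 and the placebo group is about -30"%), SD 35, significance level 0.025, 36 completers per group, stated power 90%: SAP 4.
- Group sizes 44 and 34 (44 + 34 = 78 treated) and 38 placebo: Amendment 6 rationale, Tables 3.2 and 3.2.1.

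**Assumption not in the documents**

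- r is the correlation, among treated patients, between exposure and improvement in fat when the drug itself does nothing. I use 0 to 0.4.

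**Step 1: reproduce the plan's figure.** A two-sample t-test (noncentral t, two-sided 0.025, 36 versus 36, difference 30, SD 35) has power 0.908. The stated 90% reproduces, so nothing here rests on a sample-size error.

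**Step 2: bias in closed form.** Take the top fraction q of treated patients on a normally distributed marker. With no drug effect, the expected difference from placebo is

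- high group: −SD × r × φ(c)/q
- low group: +SD × r × φ(c)/(1 − q)

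Here q = 44/78 = 0.564, c is the cut on the standard normal scale (−0.161), and φ(c) = 0.394. So φ(c)/q = 0.698 and φ(c)/(1 − q) = 0.903.

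- High group: −35 × 0.698 × r = −24.4r
- Low group: +35 × 0.903 × r = +31.6r

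**Step 3: rejection rates.** I simulated 40,000 null trials per setting. Each group was tested against all 38 placebo patients with a two-sided t-test at 5%.

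| r (assumed) | High vs placebo, points | Rejects | Low vs placebo, points | Rejects | All 78 vs 38 rejects |
|---|---|---|---|---|---|
| 0 | 0 | 5.0% | 0 | 5.0% | 5.1% |
| 0.2 | −4.9 | 9.6% | +6.3 | 11.6% | 4.9% |
| 0.3 | −7.3 | 15.8% | +9.5 | 21.0% | 5.0% |
| 0.4 | −9.8 | 24.9% | +12.6 | 33.5% | 4.9% |

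The points are closed-form values; simulated means agree to within about 0.2 (at r = 0.4, −9.7 and +12.5). Negative favours drug.

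**Step 4: where the bias comes from.** If the same marker stratum could be taken in both arms (r = 0.3, 44 versus 21), the rejection rate is 5.3% and the bias is about 0. The problem is one-sided selection, not small groups.

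**Step 5: high versus low within the active arm.** In the same null trials this contrast rejects 29%, 56% and 83% of the time at r = 0.2, 0.3 and 0.4. Dropping placebo removes the misleading contrast but not the confounding. This matters for the fix.

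**The case against.** **The mechanism may be weak for exposure.** The Week 2 AUC follows a dose given in the clinic. With the SAP 3.9 elimination constant of 0.292 per hour, the half-life is ln 2/0.292 = 2.4 h and carry-over at 24 h is exp(−0.292 × 24), about 0.1%. Earlier adherence therefore barely moves that AUC, and it precedes most of the 12 weeks in which weight could change. This stands, and it argues for the lower end of the range for AUC. It does not bring the correlation to zero: patient factors that affect both drug handling and liver fat remain, and SAP 3.7.2 also brings in concentrations at later visits.

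**SHBG is different from exposure.** A reader might infer that high-SHBG treated patients are tested against all placebo. The documents do not establish that. SHBG is measured in both arms, so placebo could be split by it, and the rationale says only that the comparison was relative to placebo. What stands is that the comparator is unstated and that SHBG change is measured at, or over, the outcome period. If the drug itself raises SHBG, a split placebo arm would still not be comparable.

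**The SAP already plans correlation work.** SAP 3.7.5 plans Spearman correlations of MRI-PDFF change with SHBG change and weight loss, by arm. SAP 3.7.6 plans exposure–efficacy correlations. This is correct, and the fix should build on both. Neither section withdraws the tests against placebo.

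**Many repeats are labelled exploratory.** This is true of the biopsy, enzyme, lipid and fibrosis-marker analyses. The label concerns multiplicity. It does not tell the reader that the groups are non-randomised.

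**Conclusion.** The concern holds for the exposure groups. Groups defined only in treated patients are set against the whole placebo arm with p-values on the primary endpoint, and nothing in SAP 3.7.2 marks the contrast as non-randomised. At assumed correlations of 0.2 to 0.4, the false benefit in the high group is about 5 to 10 points against a planning effect of 30, and the false harm in the low group is about 6 to 12.5 points. These sizes rest on the plan's SD of 35, a normally distributed marker and a correlation that the documents do not give.

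Two stronger readings are not supported:

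- That the primary result is compromised. The comparison of all active patients with placebo keeps its 5% level throughout.
- That the exposure p-values are necessarily wrong, or always lean toward the drug. At zero correlation there is no bias, and in the low group the bias runs against the drug.

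The same caution applies to the SHBG groups, subject to the unstated comparator, and to treated MRI responders versus all placebo, where group membership is itself defined by treatment outcome.

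**What to change.** - Keep all-randomised active versus placebo as the only inferential comparison for MRI-PDFF.
- In SAP 3.7.2, 3.7.2.4, 3.7.2.6, 3.7.3 and 3.7.4, separate baseline subgroups from post-randomisation groups. Present exposure, SHBG and MRI-responder groups against placebo as non-randomised and descriptive, without p-values.
- State whether placebo is split by SHBG or used whole.
- State one definition of the exposure variable; SAP 3.7.2 and the Amendment 6 rationale describe it differently.
- Extend SAP 3.7.5 and 3.7.6 with a within-active-arm model using continuous AUC, adjusted for baseline covariates such as baseline PDFF and baseline weight. Weight change is itself post-randomisation, so use it only in a sensitivity analysis. Report SHBG change as an association, not a causal effect. State that unmeasured confounding remains, as Step 5 shows.

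The cost is SAP wording and one regression per endpoint. The downside is that the high-exposure versus placebo p-values are lost. The Week 12 tables were run in November 2017, before SAP version 1.0 was approved in May 2018, so for Week 12 the change affects how results are reported.
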